- Urine dipstick pregnancy test in WOCBP. At Visit 1, FSH assessment will be performed for women not of childbearing potential.
- For presence of alcohol or prohibited substances, e.g. cocaine
- Subjects will be given access to an eDiary and given instructions on how to use it at study enrolment. The eDiary will include the RCS, NRS pain scale, record of attacks (start time and finish time and date), IMP administration timepoints and reminders to subject.
- eDiaries will be completed for the final time and then “closed” so that no further data are entered.
- IMP administered together with food at the study site.
- Subjects bring a urine sample (first urination of the day) from home to the study site in the container provided.
- Predefined biomarkers (including hsCRP, Endothelin-1, sE-selectin, xICAM1, TNF, IL-1b, IL-4, IL-6, IL-10, s-PECAM1 CXCL-4, CD40L and von Willebrand factor).
- Two cold challenges will be performed, one pre- and another 180 mins post-IMP administration, see Appendix 2.1.
- Analysis of surface markers of platelet activation performed at a local laboratory.
- Two D-OCT assessments will be performed, one pre- and another 175 mins post-IMP administration
- WOCBP will receive a home pregnancy test to be used 35-40 days after their last dose of IMP.

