**APPENDIX 8: METHODS OF ASSESSMENT FOR EFFICACY ENDPOINTS**

Assessment	Description	Evaluation	Visit	Method of Collection
RP attack (eDiary)	A PRO Number and duration of attacks (for each attack: date, start time, stop time). Pain NRS for each attack.	-Mean number of RP attack during 7 days prior to Visit 4 compared with the mean number of RP attacks 7 days prior to Visit 2. -Cumulative duration of RP attacks during 7 days prior to Visit 4 minus the cumulative duration of RP attack during 7 days prior to Visit 4. - Mean change in NRS during 7 days prior to Visit 4 minus the mean NRS during 7 days prior to Visit 2	Daily from Visit 1 through to Visit 5	eDiary
Raynaud's Condition Score (RCS)	A PRO RCS is a validated numeric rating scale 0-10 (0 = No difficulty; 10 = Extreme difficulty) answering the question "What difficulty did you have today with your Raynaud's condition". To measure disease activity and Functional status	Mean score during 7 days prior to Visit 4 compared with mean score during 7 days prior to Visit 2.	Daily from Visit 1 through to Visit 5	eDiary
Physician Global Impression of Change	The clinician is answering the question "Considering all the ways in which Raynaud's symptoms affect your patient, compared to the start of treatment, how do you rate your patient's Raynaud's?" using a scale of; 1 = much better, 2 = a little better, 3 = no change, 4 = a little worse, 5= much worse.	The score at Visit 4 to be used	Visit 4	eCRF
Patient Global Impression of Change	A PRO The subject is answering the question "Considering all the ways in which Raynaud's symptoms affect you, compared to the start of treatment, how do you	The score at Visit 4 to be used	Visit 4	eDiary

Assessment	Description	Evaluation	Visit	Method of Collection
	rate your Raynaud's currently?" using a scale of; 1 = much better, 2 = a little better, 3 = no change, 4 = a little worse, 5 = much worse.			
ASRAP Questionnaire	A PRO	A newly developed outcome measure to assess the impact of RP physically and mentally, and how it impacts on subjects' daily life.	Visit 2 Visit 3 Visit 4 Visit 5	Paper

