**Raynaud’s Attack Form:**

Date of attack: DD/MMM/YY [Auto]

What time did your Raynaud attack start? HH-MM [24hr clock]

What time did your Raynaud attack stop? HH-MM [24hr clock]

Please record the score that best indicates the pain you experienced with **this** attack: \_\_\_\_\_

0=No pain

10=Worst imaginable pain

Thank you for completing this assessment.

To report another Raynaud Attack, please start another Raynaud Attack Form after submitting this form, on the next page.

---

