5.1.1 Diary: Number of RP attacks

RP attacks in the daily diary

RP attacks are captured in the diary. For each RP attack the date, start time, stop time and the experienced pain (scale of 0 (No pain) to 10 (worst imaginable pain)) is captured. If an RP attack continues into the next day, the RP attack is counted on the date the attack started.

In addition to the daily entry of RP attacks in the diary, the diary is organized in such a way that patients are asked, through the previous attack details form, whether they had any RP attacks on the previous day:

- Did you have any attacks yesterday (CEPERF=Yes/No)
- Did you record them all in the diary (CECONF=Yes/No)

The replies to these questions are used for the interpretation of the RP attacks recorded in the diary in the following way:

Statistical Analysis Plan	Version 2.0		Page 17 of 18
Sponsor	Gesynta Pharma AB	Protocol No	GS-2001

If the patient answers (CEPERF=No) or the patient answers (CEPERF=Yes and CECONF=Yes), it is assumed that RP attacks on the previous day are recorded as instructed.

If the patient confirms both questions (CEPERF=Yes and CECONF=Yes), it is assumed that RP attacks on the previous day are recorded as instructed.

If the patient answers CEPERF=Yes and CECONF=No, and any RP attacks are recorded on the previous day, it is assumed that RP attacks on the previous day are recorded as instructed.

If the patient answers CEPERF=Yes and CECONF=No, and no RP attacks are recorded on the previous day, it is assumed the RP attacks on the previous day are confirmed missing.

Missing value imputation to come to number of RP attacks in the 7 days preceding a visit

For each day, starting during the baseline diary week, the number of recorded RP attacks as defined above and the number of days with confirmed RP attack information, are counted.

For the baseline week and for week 4 the number of daily attacks in the 7 most recent days before a visit (Day 1 and Day 28 (-2/+1)), will be derived by calculating the mean number of daily RP attacks on the days with RP attack information in the 7 most recent days and subsequently imputing this mean on the days with confirmed missing RP attack information in the 7 most recent days in the following way:

- 1) Summing the number of confirmed RP attacks in the 7 most recent days before a visit (total number of confirmed RP attacks)

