Blinded Diary review showed that for RP attack duration, some patients entered a stop date/time of an RP attack that was before the start date/time of the RP attack. For these entries the following rules will be applied:

- For the overlapping events – the latest entered event of the overlapping ones (using SEQ no. in the database) will be used. The other entry will not be used in any attack reporting (RPA, Pain, duration i.e. not be counted at all). The information will be kept in the raw data-sets.
- If stop time was before start time – duration will be set to missing, but attacks will as be counted as confirmed attacks in RPA and Pain derivations

Statistical Analysis Plan	Version 2.0		Page 21 of 22
Sponsor	Gesyntha Pharma AB	Protocol No	GS-2001

- If recall period > 1 day this will be a minor protocol deviation, recalled data will not be excluded from the analysis.

Blinded review of the derived cumulative and mean RP attack duration as derived of the 7 most recent days prior to a visit showed that the derived values have a skewed distribution. For that reason, the evaluation of cumulative RP attack duration and mean RP attack duration will be done on natural log scale.

For each patient change in log-transformed cumulated RP attack duration and log-transformed mean RP attack duration will be derived as follows:

- Change = LN(cumulative RP attack duration prior to week 4 visit) – LN(cumulative RP attack duration prior to baseline visit)
- Change = LN(mean RP attack duration prior to week 4 visit) - LN(mean RP attack duration prior to baseline visit)

The analysis of the mean change in LN(cumulative duration of RP attacks) and mean change in LN (mean RP attack duration) will be similar to the analysis of the primary endpoint.

Descriptive statistics will be provided for the cumulative RP durations and mean RP attack durations on both the absolute and the log-transformed scales. After summarizing the log-transformed values, the back-transformed values of the descriptive statistics of the log-transformed values and of the descriptives of the changes on log-scale will be created for these parameters at baseline visit and week 4 visit.

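### SAP 5.2.3 has no midnight exception: on the documented diary form, an attack that runs past midnight is valid but loses its duration

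*SAP*

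**What the plan says.** The Raynaud's Attack Form in Protocol Appendix 10 has one date field, filled automatically ("Date of attack: DD/MMM/YY [Auto"), and two clock times: "What time did your Raynaud attack start? HH-MM [24hr clock" and "What time did your Raynaud attack stop? HH-MM [24hr clock". Three other places list the same fields:

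- the eDiary footnote to Protocol Appendix 2: "record of attacks (start time and finish time and date"
- Protocol Appendix 8: "for each attack: date, start time, stop time"
- SAP 5.1.1: "For each RP attack the date, start time, stop time and the experienced pain"

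None of them shows a second date for the end of the attack.

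SAP 5.1.1 foresees attacks that cross midnight and settles how to count them: "If an RP attack continues into the next day, the RP attack is counted on the date the attack started". It gives no rule for their length.

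SAP 5.2.3 reports that blinded diary review found attacks that ended before they began. For a stop time earlier than the start time, "duration will be set to missing, but attacks will as be counted as confirmed attacks in RPA and Pain derivations". The sentence that introduces this rule attaches a date to both the start and the stop.

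The same section derives cumulative duration in three steps: sum the durations, divide by the number of confirmed attacks, then multiply by the weekly attack number from 5.1.1. The endpoint is the change on the natural log scale. Duration is third in the key secondary test order, after pain and the Raynaud's Condition Score (RCS).

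**The concern.** One section of the SAP treats an attack that runs past midnight as valid. Another, read against the documented form, treats the same record as an entry error and discards its length. Some of the entries flagged at blinded review may therefore be correct.

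The loss is not random with respect to length. For a given pattern of start times, a longer attack is more likely to reach midnight, so the discarded attacks are longer on average than those kept. Cumulative duration, and the mean duration analysed with it, would then be too low.

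The step 2 denominator matters as well. The rule keeps these attacks as confirmed for the count and for pain, and does not say whether they also stay in the duration denominator. If they stay, each enters as zero minutes. If they leave, step 3 gives each one the mean of the subject's other attacks.

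**Working it through.** The plan gives no figure for attack duration or for time of day, so there is nothing of its own to reproduce. The sample size of 26 per group rests on attack number and is not affected.

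**What the form does to one attack.** Start 23:40, stop 00:20, one date. The raw difference is 20 − 1,420 = −1,400 minutes, so the rule applies. Adding 24 hours gives −1,400 + 1,440 = 40 minutes, the true length.

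**One diary week (assumed).** Thirteen attacks of 20 minutes and one from 23:40 to 00:30 (50 minutes). The true total is 13 × 20 + 50 = 310 minutes.

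- Attack stays in the denominator: 260/14 × 14 = 260 minutes, −16.1%.
- Attack leaves the denominator: 260/13 × 14 = 280 minutes, −9.7%.
- If the crossing attack lasts only 20 minutes, the true total is 280 minutes and the errors are −7.1% and 0%.

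**Average loss under a simple model (all inputs assumed).** Durations are exponential with mean m. Starts are uniform over T = 960 minutes, and the window ends g minutes before midnight. Ignoring the negligible far tail:

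- share of attacks crossing: p = (m/T) × exp(−g/m)
- share of attack time in those attacks: s = ((g + 2m)/T) × exp(−g/m)
- shortfall in cumulative duration if they stay in the denominator: s
- shortfall if they leave it: 1 − (1 − s)/(1 − p)

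| Mean m | Starts end at | p | s (shortfall if kept) | Shortfall if removed |
|---|---|---|---|---|
| 30 min | midnight (g = 0) | 30/960 = 3.1% | 60/960 = 6.3% | 1 − 0.9375/0.96875 = 3.2% |
| 60 min | midnight (g = 0) | 60/960 = 6.3% | 120/960 = 12.5% | 1 − 0.875/0.9375 = 6.7% |
| 30 min | 23:00 (g = 60) | 3.125% × exp(−2) = 0.4% | (120/960) × exp(−2) = 1.7% | 1 − 0.9831/0.9958 = 1.3% |
| 60 min | 23:00 (g = 60) | 6.25% × exp(−1) = 2.3% | (180/960) × exp(−1) = 6.9% | 1 − 0.9310/0.9770 = 4.7% |

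**How long the affected attacks are.** Their mean length relative to all attacks is s/p. For starts running to midnight this is 6.25/3.125 = 2 at either mean. Simulation with lognormal durations (medians 15 to 60 minutes, log-SD 0.8 to 1.0) and starts uniform over 24 hours gave a ratio of 1.9 to 2.7. In those runs 31% to 39% of crossing attacks were in the longest tenth of all attacks, and 16% to 22% were shorter than the median.

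**The case against.** The strongest reply is that the premise may be false. The introductory sentence in SAP 5.2.3 was written after a look at the blinded data, and it speaks of a date with both the stop and the start. If the database holds a stop date, 23:40 to 00:20 is in the right order and the rule never touches it. This stands as a reason to check. It does not close the point: four descriptions of the data show a single date, the operative bullet compares times only, and the date-time could have been built from that single date.

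A reader might infer that the rule removes the longest attacks. The documents do not say so, and the simulation does not support it as a general statement, because a short attack just before midnight also crosses. Only when no attack started after 23:00 were most crossing attacks (61% to 100%) in the longest tenth, and they were then 0.1% to 5.5% of all attacks.

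A reader might also infer that each affected attack is scored as zero. That is one reading of step 2. The SAP names only the count and pain when it keeps these attacks as confirmed, so the other reading is equally open.

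Finally, a reader might infer a biased treatment effect. The rule is the same in both arms and at both visits, and a constant proportional loss cancels in a difference of logs. Suppose treatment shortened mean attacks from 30 to 20 minutes, with starts running to midnight and attacks kept in the denominator. The losses would be 6.25% and 2 × 20/960 = 4.17%. The log change would move from ln(20/30) = −0.405 to −0.405 + ln(0.9583/0.9375) = −0.383, a small attenuation. This objection largely stands.

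**Conclusion.** The point holds in a limited form. On the form as documented, SAP 5.2.3 sets a valid duration to missing whenever an attack crosses midnight, although SAP 5.1.1 accepts such attacks. Whether this happens in the data depends on whether a stop date is stored, which the documents leave open.

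If none is stored, about 0.4% to 6.3% of attacks and 1.7% to 12.5% of attack time lose their duration under the assumed model. If starts run to midnight, cumulative duration is too low by about 6.3% to 12.5% when these attacks stay in the step 2 denominator, and by about 3.2% to 6.7% when they leave it. These figures rest wholly on assumed durations and start times. Single subject-weeks can be hit harder, as the worked week shows.

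The effect is confined to duration, which is formally tested only if the primary endpoint, pain and RCS all succeed. Attack count, pain and RCS are not affected. Partial cancellation between visits and arms is likely, and the direction of any bias in the treatment comparison is not established.

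**What to change.** Amend SAP 5.2.3 before unblinding:

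1. State whether a stop date is stored for each attack. If it is, derive duration from full date-times.
2. If it is not, and the stop clock time is earlier than the start clock time, add 24 hours to the stop. Keep the duration only if it is within an absolute maximum fixed at blinded review and does not overlap the next recorded attack. Otherwise set the duration to missing and keep counting the attack, as now.
3. In step 2, divide by the number of confirmed attacks with a non-missing duration.
4. Report the number of affected attacks by arm and visit.

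The absolute maximum is needed. A swapped entry such as 14:30 to 14:10 would become 23 hours 40 minutes, and the overlap check alone may not catch it in a subject with about one attack a day, which the entry criterion of 7 attacks a week allows.

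The cost is a few lines of text and a small programming change. The 24-hour rule has no effect if a stop date exists. The downside is that a few swapped entries near midnight may receive a wrong duration, limited by the maximum.

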5.3 Exploratory objectives and endpoints

5.3.1 Patient Global Impression of Change at week 4.

Patient Global Impression of Change at week 4 will be presented for the number and percentage of subjects providing the categorized week 4 responses for each treatment group.

The statistical analysis will consist of a Cochran-Mantel-Haenszel analysis comparing treatment groups adjusting for the stratification factor.

5.3.2 Physician Global Impression of Change at week 4.

Physician Global Impression of Change at week 4 will be presented for the number and percentage of subjects providing the categorized week 4 responses for each treatment group.

The statistical analysis will consist of a Cochran-Mantel-Haenszel analysis comparing treatment groups adjusting for the stratification factor.

5.3.3 Mean change in ASRAP Questionnaire score from baseline to week 4

The ASRAP questionnaire score (reporting on the past 7 days) results for each patient in the ASRAP total score, the sum of all items scores.

The analysis of the Mean ASRAP Questionnaire total score will be similar to the analysis of the primary efficacy endpoint using observed data.

Statistical Analysis Plan	Version 2.0		Page 22 of 23
Sponsor	Gesyntha Pharma AB	Protocol No	GS-2001

Descriptive statistics of the observed cases and mean change from baseline will be created for the ASRAP Questionnaire total score at baseline, week 2, week 4 and at follow-up.

5.3.4 Mean change from baseline to week 4 in peripheral blood flow prior to cold challenge and IMP administration

The following parameters for peripheral blood flow prior to cold challenge are defined:

- Mean temperature of all eight fingers prior to cold challenge (MTEMPALL)
- Mean Distal Dorsal Difference (DDD) of all eight fingers prior to cold challenge (MDDDF)

Descriptive statistics of the observed cases and change from baseline will be created for these parameters at baseline (first assessment at visit 2, $t < 0$) and week 4 ($t = -5$ min).

The analysis of the peripheral blood flow will be similar to the analysis of the primary efficacy endpoint using observed data.

5.3.5 Mean change in peripheral blood flow from pre-IMP to post-IMP administration at Visit 2

The following parameters for peripheral blood flow from pre-IMP to post-IMP administration are defined:

- Mean temperature of all eight finger after IMP administration but prior to cold challenge at visit 2 (MTEMPALL)
- Mean DDD of all eight fingers after IMP administration but prior to cold challenge at visit 2 (MDDDF)

Descriptive statistics of the observed cases and change from baseline will be created for these parameters at pre-IMP (Baseline, Session 1, $t = 80$ to 120 min) and post-IMP (Session 2, $t = 0$ to 150 min).

The analysis of the peripheral blood flow will be similar to the analysis of the primary efficacy endpoint using observed data.

5.3.6 Mean change in recovery of peripheral blood flow after cold challenge from pre-IMP to post-IMP administration at Visit 2

The following parameters for recovery of peripheral blood flow after cold challenge from pre-IMP to post-IMP administration are defined:

- Recovery of peripheral blood flow, in terms of mean LN(AUC temp at all eight fingers after cold challenge and after IMP administration) at Visit 2. (Session 2, LN(MAUC8))
- Mean LN(maximum temperature of all eight fingers after cold challenge and after IMP administration) at Visit 2. (Session 2, LN(MMAX8))

After summarizing the log-transformed values, the back-transformed values of the descriptive statistics of the log-transformed values and of the descriptives of the changes on log-scale will be created for these parameters at pre-IMP (Baseline, Session 1) and post-IMP (Session 2).

Statistical Analysis Plan	Version 2.0		Page 23 of 24
Sponsor	Gesynta Pharma AB	Protocol No	GS-2001

The analysis of the peripheral blood flow will be similar to the analysis of the primary efficacy endpoint using observed data.

5.3.7 Mean change from baseline to week 4 in recovery of peripheral blood flow after cold challenge.

The following parameters for recovery of peripheral blood flow after cold challenge are defined:

- Recovery of peripheral blood flow, in terms of mean LN(AUC temp all eight fingers after cold challenge) at visit 4.
- Mean LN(maximum temperature of all eight fingers after cold challenge) at Visit 4.

After summarizing the log-transformed values, the back-transformed values of the descriptive statistics of the log-transformed values and of the descriptives of the changes on log-scale will be created for these parameters at pre-IMP (Baseline, Session 1) and post-IMP (Visit 4).

The analysis of the peripheral blood flow will be similar to the analysis of the primary efficacy endpoint using observed data.

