### 6.3.2 Pharmacodynamics

- PGE2 levels in whole blood: In up to 30 subjects blood samples will be drawn at Visit 2 and Visit 4 pre-IMP administration to assess change in PGE2 level in whole blood *ex vivo* from baseline to week 4.
- Levels of PGEM, PGIM and TXM in urine: Spot morning urine samples will be collected by subjects at home and brought to the study site at Visit 2 and Visit 4 for assessment to determine change in levels of PGEM, PGIM, and TXM in urine from baseline to week 4.
- Biomarkers for inflammation and endothelium dysfunction: Blood samples will be collected from all subjects at Visit 2 and Visit 4 pre-IMP administration for analysis of hsCRP, Endothelin-1, sE-selectin, ICAM1, TNF, IL-1b, IL-4, IL-6, IL-10, s-PECAM1 CXCL-4, CD40L and von Willebrand factor to determine change in levels of biomarkers in blood/plasma from baseline to week 4.
- Expression of platelet surface markers: In up to 20 subjects blood samples will be drawn at Visit 2 and Visit 4 pre-IMP administration for analysis of surface markers of platelet activation by FACS analysis to determine change from baseline to week 4.
- Microvascular volume in skin/nailfold: At one pre-defined site, microvascular volume in skin/nailfold (see [APPENDIX 6](#) and [APPENDIX 7](#)) will be performed on consenting subjects twice at Visit 2 and Visit 4 (pre-IMP administration and at expected Cmax by D-OCT), and once at Visit 3 and Visit 5, to determine change in microvascular volume from baseline to week 4.
- Collection of blood and urine samples for Biobank storage: One urine sample each from Visit 2 and Visit 4 and four plasma samples, two from Visit 2 and Visit 4 will be stored in a Biobank for up to 3 years after study end for potential future analysis of inflammatory biomarkers and biomarkers for endothelial dysfunction.

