**DETAILED SCHEDULE OF ASSESSMENTS COLD CHALLENGE/THERMOGRAPHY – VISIT 2**

The detailed schedule of assessment below describes the **additional** assessments at Visit 2 if the subject is enrolled to Cold Challenge.

	Session 1 										Session 2 				
	Minutes (time window +/- 5 minutes, exact time recorded in eCRF)														
	0 (0-15)	30	80	100	120 	0	30	60	90	120	150	170	175	180 (180-195)	200
Cold Challenge / Thermography															
Finger temperature															
Cold challenge with thermography every 15 seconds	X														
Thermography			X	X	X	X	X	X	X	X	X	X	X	X	

 Session 1 is conducted after randomization and prior to IMP administration.

 Session 2 starts at the same time as IMP administration, see DETAILED SCHEDULE OF ASSESSMENTS – VISIT 2.

 Estimated that skin temperature has returned to normal at 120 minutes, otherwise wait until it has returned to normal.

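### SAP 5.3.5 counts the image taken at dosing as post-dose, closes the window before expected Cmax, and names no single value per subject for the ANCOVA

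*SAP*

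**What the plan says.** The acute change in peripheral blood flow at Visit 2 is one of four endpoints for the secondary objective (Protocol Table 2.1, SAP 1.2). The SAP analyses it in section 5.3, among the exploratory endpoints.

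- **Parameter.** SAP 5.3.5 defines the first parameter as "Mean temperature of all eight finger after IMP administration but prior to cold challenge at visit 2 (MTEMPALL". The distal dorsal difference is defined in the same way.
- **Windows.** The same section asks for descriptive statistics at "pre-IMP (Baseline, Session 1, $t = 80$ to 120 min) and post-IMP (Session 2, $t = 0$ to 150 min".
- **Clock.** The footnote to the Visit 2 cold challenge schedule (Protocol Appendix 3) says "Session 2 starts at the same time as IMP administration". The column heading gives "Minutes (time window +/- 5 minutes, exact time recorded in eCRF".
- **Rewarming.** Another footnote to that schedule, on the 120-min point of Session 1, says "Estimated that skin temperature has returned to normal at 120 minutes, otherwise wait until it has returned to normal".
- **Expected peak.** Protocol 6.3.2 times the paired D-OCT scans at Visits 2 and 4 as "pre-IMP administration and at expected C max by D-OCT". The Appendix 2 footnote gives the clock time: "Two D-OCT assessments will be performed, one pre- and another 175 mins post-IMP administration".
- **Second challenge.** Appendix 2 also states "Two cold challenges will be performed, one pre- and another 180 mins post-IMP administration". Under Appendix 5, a thermal image of both hands is taken just before each challenge.
- **Model.** SAP 5.3.5 refers back to the primary analysis, on observed data. That analysis is an ANCOVA of change with stratum, treatment and baseline (SAP 5.1.4).

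**The concern.** Three things do not fit together.

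1. The parameter is defined as measured after dosing, yet its window opens at the minute of dosing. That image belongs on the pre-dose side.
2. The window closes 25 min before expected peak concentration, although an image that meets the SAP's own definition is taken later, just before the second challenge.
3. An ANCOVA modelled on the primary needs one pre-dose and one post-dose value per subject. The SAP gives two ranges of times and no rule for reducing them. The word mean in the parameter names refers to the eight fingers, not to time.

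The pre-dose side is also loosely set. SAP 4.1.1 takes as baseline the latest available value before the first dose, whereas 5.3.5 uses a 40-min range. Its 80- and 100-min images precede the protocol's estimate of when skin temperature is back to normal.

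At stake is the sensitivity and clarity of an acute read-out in an estimated 50 subjects. An unstated summary rule also leaves a choice that could be made after the results are seen.

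**Working it through.** **Stated figures.** The documents give no effect size, SD or power for this endpoint, so there is no figure to reproduce. For context, 50 subjects at 1:1 is 25 per arm. A two-sided t-test at 0.05 then has 80% power for about 0.81 SD. That figure describes the sample size, not the defect.

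**Step 1: minute 0.** Let e(t) be the true between-arm effect at minute t, with e(0) = 0 because t = 0 is dosing. Let S be the sum of e(t) over 30, 60, 90, 120 and 150 min. Assume equal-weight averaging, which the SAP does not state.

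- With minute 0: S/6. Without it: S/5.
- Ratio: (S/6)/(S/5) = 5/6 = 83.3%, a loss of 16.7% for any curve.

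**Step 2: does averaging an extra image offset this?** Assume equal variances and a common correlation r between images (residual, after baseline adjustment). The variance of a mean of n images is proportional to (1 + (n-1)r)/n. Dropping minute 0 multiplies the standardised effect by 1.2 × √[5(1+5r) / (6(1+4r))].

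- r = 0: 1.2 × √(5/6) = 1.10
- r = 1: 1.2 × √(30/30) = 1.20

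So dropping it gains 10% to 20% for any r from 0 to 1.

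**Step 3: stopping at 150 min.** The documents give no time course of effect, so several curves are assumed. Entries are the equal-weight average as a share of the effect at 175 min. In the last column, 175 min stands in for the image before the second challenge.

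| Assumed curve | 0-150 | 30-150 | 30-150 plus 175 |
|---|---|---|---|
| Full effect from the 30-min image | 83% | 100% | 100% |
| Square-root rise | 58% | 69% | 75% |
| Linear rise | 43% | 51% | 60% |
| Linear after a 30-min lag | 34% | 41% | 51% |
| Quadratic rise | 27% | 32% | 44% |

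For the linear row, the mean of 0, 30, ..., 150 is 75, and 75/175 = 0.43. In every row the first column is 5/6 of the second. The rest of the shortfall depends entirely on the curve.

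**Step 4: the pre-dose window.** Session 1 precedes dosing in both randomised arms. A simulation used 25 per arm, a true difference of 1.0, between-subject SD 2.0, within-subject SD 1.0, a rewarming deficit varying between subjects, and 4,000 runs. It fitted a baseline-adjusted ANCOVA without stratum. All these values are assumptions.

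| Mean deficit in pre-dose window (°C) | ANCOVA difference | Its SE | Placebo change | Active change |
|---|---|---|---|---|
| 0 | 0.99 | 0.388 | 0.0 | 1.0 |
| 0.5 | 1.00 | 0.387 | 0.5 | 1.5 |
| 1.0 | 1.00 | 0.392 | 1.0 | 2.0 |
| 2.0 | 1.01 | 0.441 | 2.0 | 3.0 |

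The between-arm difference does not move. The within-arm change rises equally in both arms, and precision falls visibly only at the largest deficit.

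**Step 5: analysis by time point.** With images at 0, 30, ..., 150 min this gives six tests for each of two parameters, 12 in all. The two at minute 0 can show no effect, and no time point is named as decisive.

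**The case against.** The strongest reply is that the SAP never says the images are averaged. The window sits in a sentence about descriptive statistics, and if results are given by time point there is no dilution. That is correct, and it makes the one-sixth figure conditional. It does not remove the wrong label on minute 0, and it leaves open which pre-dose and post-dose values the ANCOVA uses.

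A second reply is that expected Cmax is a concentration peak. Protocol 1.3 and 3.3 report full target inhibition at low doses and complete inhibition of PGE2 synthesis at single doses from 40 mg, so an effect might appear well before Cmax. On the other hand, urinary PGIM rose with dose. The time course on finger temperature is therefore unknown. This stands: no single figure for the loss from stopping at 150 min can be defended.

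A reader might infer that the plan throws away half the effect, since under a linear rise the 0-150 average is 43% of the 175-min effect against 86% at 150 min alone. That needs both the pooling rule and the linear curve, and the documents state neither.

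A reader might also infer that the pre-dose window dilutes the drug effect because the hands are still rewarming. Step 4 shows why it does not. The footnote, moreover, only estimates a return to normal at 120 min and does not say that hands are abnormal at 80 or 100 min. The 120-min image is itself in the window.

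Finally, this is not the only acute read-out. SAP 5.3.6 analyses recovery after the 180-min challenge and is unaffected.

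**Conclusion.** The narrow point holds. SAP 5.3.5 labels a dosing-time image post-IMP and so contradicts its own definition. It stops short of a later image that meets that definition and lies near expected Cmax, and it gives no rule for one value per subject.

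If the six images are pooled equally, keeping minute 0 costs one sixth of the averaged effect whatever the curve. The 0-150 average is about 27% to 83% of the 175-min effect across the assumed curves, a range too wide to support one headline figure.

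The pre-dose window is a lesser matter. It departs from SAP 4.1.1, may add noise, and could make residual rewarming look like improvement in both arms. It does not bias the comparison between them.

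The endpoint is supportive and its p-values are nominal, so neither the primary conclusion nor the key secondary hierarchy is affected. This is a worthwhile improvement, not a threat to the trial.

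**What to change.** Amend SAP 5.3.5 before unblinding:

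- **Pre-IMP value:** the last image before or at dosing, once skin temperature has returned to normal (Session 1 at 120 min or later, or Session 2 minute 0). This also brings the section into line with SAP 4.1.1.
- **Post-IMP window:** start at 30 min and extend to the last image before the second cold challenge.
- **Summary rule:** name one value per subject and parameter for the ANCOVA, for example a time-weighted mean over the window or one stated time point.
- **Time course:** show all images by arm descriptively.

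The removal of minute 0 is supported for any effect curve. How much weight to give late images is a judgement about the time course and should be fixed without sight of unblinded data. The cost is SAP wording only: Appendices 3 and 5 of the protocol already provide for the images, and no visit or procedure changes.
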